APPENDIX C

NCI CTC Version 4

Toxicity will be scored using NCI CTC Version 4 for toxicity and adverse event reporting. A copy of the NCI CTC Version 4can be downloaded from the CTEP homepage: (http://ctep.info.nih.gov). All appropriate treatment areas have access to a copy of the CTC Version 4

APPENDIX D

ECOG PATIENT PERFORMANCE STATUS

STATUS	KARNOFSKY	ZUBROD-ECOG- WHO	Description	
No complaints	100	0	Normal activity	
Able to carry on normal activities	90	1	Symptoms, but fully ambulatory	
Normal activity with effort	80			
Cares for self. Unable to carry on normal activity or to do active work	70	2	Symptomatic, but in bed <50% of the day	
Requires occasional assistance, but able to care for most of his needs	60			
Requires considerable assistance and frequent medical care	50	3	Needs to be in bed >50% of the day, but not bedridden	
Disabled, requires special care and assistance	40			

Severely disabled. Hospitalization indicated though death non imminent	30	4	Unable to get out of bed
Very sick. Hospitalization Necessary. Active support treatment necessary	20		
Moribund Dead	0		
Dead	U		

From: Minna J.D., Higgins G.A and Glapstein E.J. Cancer of the lung: In: DeVita V, Hellman S., Rosenberg S., (Eds.). Cancer: Principles and Practice of Oncology, Lippincott, Philadelphia, 1984, p. 536

APPENDIX E

CASE REPORT FORMS

Attached separately are the BrUOG Case Report Forms

Appendix F: Permitted medications to be used with caution Table 7 List of medications to be used with caution during treatment with BYL719

Category	Drug Name		
CYP2A6 substrates	Disulfiram, fadrozole, halothane, losigamone, methoxyflurane, nicotine, valproic acid		
Sensitive CYP2C8 substrates ²	Paclitaxel, repaglinide		
Sensitive CYP2C9 substrates ²	Phenytoin		
Sensitive CYP2C19 substrates ²	S-mephenytoin, R/S-lansoprazole, clobazam, omeprazole, tilidine		
Moderate CYP3A Inhibitors	Amprenavir, atazanavir, casopitant, cimetidine, ciprofloxacin, cyclosporine, darunavir, diltiazem, dronedarone, erythromycin, fluconazole, fosamprenavir, grapefruit juice (citrus paradisi fruit juice), imatinib, Schisandra sphenanthera ² , tofisopam, verapamil		
Moderate CYP3A Inducers	Bosentan, efavirenz, etravirine, genistein, modafinil, nafcillin, ritonavir, talviraline, thioridazine, tipranavir		
Gastric protection agents	BYL719 is characterized by a pH-dependent solubility. Medicinal products that alter the pH of the upper gastro-intestinal tract may alter the solubility of BYL719 and hence its bioavailability. These agents include, but are not limited to, proton-pump inhibitors (e.g., omeprazole), H2-antagonists (e.g., ranitidine) and antacids. BYL719 should preferably be dosed in a staggered manner, i.e., at least 1 hour before or 10 hours after dosing with a gastric protection agent. Note that some proton pump inhibitors may possibly inhibit BCRP (see below).		
BCRP inhibitors	BYL719 was identified as a substrate for the human BCRP. Co-administration of BYL719 with BCRP inhibitors may possibly increase systemic exposure and/or alter tissue uptake of oral BYL719. The treatment with BCRP inhibitors should be kept as short as possible or, if possible, fully avoided.		
Drugs with a possible risk for Torsades de Pointes / QT prolongation ⁴	Alfuzosin, amantadine, atazanavir, chloral hydrate, clozapine, dolasetron, eribulin, escitalopram, famotidine, felbamate, fingolimod, foscarnet, fosphenytoin, gatifloxacin, gemifloxacin, granisertron, iloperidone, indapamide, isradipine, lapatinib, levofloxacin, lithium, moexipril, nicardipine, nilotinib, octreotide, ofloxacin, ondansetron, oxytocin, paliperidone, pasireotide, ranolazine, risperidone, roxithromycin, sertindole, sunitinib, tamoxifen, tizanidine, venlafaxine, voriconazole, ziprasidone		
Hematopoietic growth factors	Hematopoietic growth factors (e.g. erythropoietins, G-colony stimulating factor (CSF) and GM-CSF) are not to be administered prophylactically. Use of these drugs should be reserved to patients with severe neutropenia and anemia as per the labeling of these agents or as dictated by local practice (see also the guidelines established by the American Society of Clinical Oncology (ASCO)).		
Corticosteroids	Chronic dosing of high levels of corticosteroids such as dexamethasone and prednisone are known to induce CYP3A enzymes, thereby increasing the risk		

Category	Drug Name			
	of reducing letrozole drug exposure to sub-therapeutic levels. Since corticosteroids may prolong or aggravate hyperglycemia (steroid-induced diabetes), which is a common adverse event for PI3K inhibitors such as BYL719, they should be additionally used with caution and closely monitored.			
Anticoagulation	Anticoagulants other than warfarin/coumarin derivates (Appendix 2, Table 8) or antiaggregation agents may be administered under the discretion of the investigator. However, caution is advised when BYL719 is co-administered with anti-platelet pro-drugs such as clopidogrel, ticlopidine and prasugrel, which require metabolic activation by CYP3A4, CYP2C9 and CYP2C19. BYL719 has the potential to inhibit some of these enzymes and may therefore decrease the metabolic activation and clinical efficacy of these pro-drugs. Patients using anti-platetet pro-drugs should be carefully monitored.			

¹Any drug mentioned in the above list should be contraindicated if they are excluded based on any other exclusion criteria, or as specified in Section Concomitant Medications of this guideline document or listed in Appendix G,

²Sensitive substrates: Drugs whose plasma AUC values have been shown to increase 5-fold or higher when coadministered with a potent inhibitor.

³NTI = narrow therapeutic index drugs whose exposure-response indicates that increases in their exposure levels by the concomitant use of potent inhibitors may lead to serious safety concerns (e.g., Torsades de Pointes).

⁴ Please also refer to http://crediblemeds.org/ for a comprehensive list of agents that prolong the QT interval.

Appendix G: Prohibited medications List of prohibited medications during BYL719 treatment

Category	Drug Name		
Strong CYP3A Inhibitors	Boceprevir, clarithromycin, cobicistat, conivaptan, elvitegravir, indinavir, itraconazole, ketoconazole, lopinavir, mibefradil, nefazodone, nelfinavir, posaconazole, ritonavir, saquinavir, telaprevir, telithromycin, tipranavir, troleandomycin, voriconazole		
Strong CYP3A Inducers	Avasimibe ^{2,3} , carbamazepine, mitotane, phenobarbital, phenytoin, rifabutin, rifampin (rifampicin) ³ , St. John's wort (hypericum perforatum) ³		
CYP3A substrates with NTI ¹	Alfentanil, astemizole, cisapride, cyclosporine, diergotamine (dihydroergotamine), ergotamine, fentanyl, pimozide, quinidine, sirolimus, tacrolimus, terfenadine		
Sensitive CYP3A Substrates ⁴	Alpha-dihydroergocryptine, aplaviroc, aprepitant, atorvastatin, brecanavir, brotizolam, budesonide, buspirone, capravirine, casopitant, conivaptan, darifenacin, darunavir, dasatinib, dronedarone, ebastine, eletriptan, eplerenone, everolimus, felodipine, fluticasone, indinavir, levomethadyl, lopinavir, lovastatin, lumefantrine, lurasidone, maraviroc, midazolam, neratinib, nisoldipine, perospirone, quetiapine, ridaforolimus, saquinavir, sildenafil, simvastatin, ticagrelor, tipranavir, tolvaptan, triazolam, vardenafil, vicriviroc		
Other investigational and antineoplastic therapies	Other investigational therapies should not be used while the patient is on the study. Anticancer therapy [chemotherapy, biologic or radiation therapy, and surgery (unless specified in protocol)] other than the study treatments must not be given to patients while the patient is on the study medication. If such agents are required for a patient then the patient must be discontinued from the study.		
Herbal medications	Herbal preparations/medications are prohibited throughout the study, as a potential drug-drug-interaction is always possible. These herbal medications include, but are not limited to: St. John's wort, Kava, ephedra (ma huang), gingko biloba, dehydroepiandrosterone (DHEA), yohimbe, saw palmetto, medical marijuana, and ginseng. Patients should stop using these herbal medications 7 days prior to first dose of study drug.		
Warfarin and coumarin derivatives	Therapeutic doses of warfarin sodium (Coumadin®) or any other coumarinderivative anticoagulants are prohibited in this study. Warfarin has a narrow therapeutic range and BYL719 is a possible inhibitor of CYP2C8 and 2C9, the major metabolizing enzyme of warfarin. Therapeutic anticoagulation may be accomplished using low-molecular weight heparin.		

Category	Drug Name		
Drugs with a known risk for	Amiodarone, amitriptyline (2C19), arsenic trioxide, astemizole, cepridil,		
Torsades de Pointes / QT	chloroquine, chlorpromazine, cisapride, citalopram, clarithromycin,		
prolongation ⁵	clomipramine (2C19), disopyramide, dofetilide, domperidone, dronedarone		
	(CYP3A4), droperidol, erythromycin, flecainide, halofantrine, haloperidol,		
	ibutilide, levomethadyl, mesoridazine, methadone, moxifloxacin, pentamidine,		
	pimozide, probucol, procainamide, quetiapine (3A4), quinidine, ritonavir		
	(3A4), sotalol, sparfloxacin, tacrolimus (3A4), telithromycin (3A4),		
	terfenadine, thioridazine, trazodone (3A4), vandetanib, vardenafil (3A4)		

¹NTI = narrow therapeutic index drugs whose exposure-response indicates that increases in their exposure levels by the concomitant use of potent inhibitors may lead to serious safety concerns (e.g., Torsades de Pointes)

²Herbal product

³P-gp inducer

⁴Sensitive substrates: Drugs whose plasma AUC values have been shown to increase 5-fold or higher when

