In vitro studies demonstrate that BYL719 is a time dependent inhibitor of CYP3A4(Ki 5.6 μM, Kinact 0.011 min-1). Reversible inhibition of CYP2C8 (Ki 32 μM), CYP2C9 (Ki 22 μM) and CYP2C19 (IC50 75 μM) was also observed. BYL719 may inhibit metabolic clearance of co-medications metabolized by CYP3A4, CYP2C8, CYP2C9 and CYP2C19, if sufficiently high BYL719 concentrations are achieved in vivo. Investigators, at their discretion, may administer concomitant medications known to be metabolized by or are substrates for CYP3A4/5, CYP2C8, CYP2C9 and CYP2C19. Patients receiving such medications and drugs which have a narrow therapeutic index must be carefully monitored for potential toxicity due to any individual concomitant medications. (refer to Appendix F).

Caution is advised when BYL719 is co-administered with opioid analgesics. Inhibition of opioid metabolism by CYP3A4 can lead to opioid toxicity, including fatal respiratory depression, or an enhanced risk for QTc prolongation. Patients receiving BYL719 and opioid analgesics should be carefully monitored. Synthetic opioids with clinically relevant interactions with CYP3A4 inhibitors include, but are not limited to, propoxyphene, fentanyl, alfentanyl and sufentanil. Use of alfentanyl, a sensitive CYP3A4 substrate with narrow therapeutic window, should be full avoided whenever possible. The use of methadone and levomethadyl is prohibited (refer to Appendix G).

Gastric protection agents

BYL719 is characterized by a pH-dependent solubility. Medicinal products that alter the pH of the upper gastro-intestinal tract may alter the solubility of BYL719 and hence its bioavailability. These agents include, but are not limited to, proton-pump inhibitors (PPI) (e.g., omeprazole), H₂-antagonists (e.g., ranitidine) and antacids. Due to long pharmacodynamic effect of PPIs, i.e. long-lasting reduction of gastric acid production over 36 hours, H₂-antagonists and antacids are recommend to be used over PPIs, whenever possible. Note that some proton pump inhibitors may possibly also inhibit BCRP (refer to Appendix F).

BYL719 should preferably be dosed in a staggered manner, i.e., at least 1 hour before or 10 hours after dosing with a gastric protection agent.

BCRP inhibitors

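### Section 4.2.1 softens Appendix G's ban on alfentanil and is silent on its ban on fentanyl, in a paragraph about fatal opioid toxicity

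*Combined protocol and SAP*

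**What the plan says.** Appendix G is the list of medications prohibited during BYL719. Its row for CYP3A substrates with a narrow therapeutic index reads "Alfentanil, astemizole, cisapride, cyclosporine, diergotamine (dihydroergotamine), ergotamine, fentanyl, pimozide, quinidine, sirolimus, tacrolimus, terfenadine". Methadone and levomethadyl appear in a different row, for drugs with a known risk of Torsades de Pointes (TdP).

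Section 4.2.1, on permitted concomitant therapy, deals with the same opioids under CYP450 substrates:

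- On the interacting opioids: "Synthetic opioids with clinically relevant interactions with CYP3A4 inhibitors include, but are not limited to, propoxyphene, fentanyl, alfentanyl and sufentanil".
- On what to do: "Patients receiving BYL719 and opioid analgesics should be carefully monitored".
- On alfentanil, spelled differently there: "Use of alfentanyl, a sensitive CYP3A4 substrate with narrow therapeutic window, should be full avoided whenever possible".
- On outright bans: "The use of methadone and levomethadyl is prohibited (refer to Appendix G".

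The paragraph before it is more general: "Investigators, at their discretion, may administer concomitant medications known to be metabolized by or are substrates for CYP3A4/5" (and certain CYP2C enzymes). It adds that patients receiving such medications and "drugs which have a narrow therapeutic index must be carefully monitored for potential toxicity", and it refers the reader to Appendix F, the list of drugs permitted with caution.

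Two other places bear on precedence. The opening of Section 4.2 makes its general permission subject to the prohibitions in Appendices F and G. Exclusion 3.2.12 bars any Appendix G drug at entry.

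**The concern.** A clinician who wants to know whether a patient on BYL719 may have an opioid will go to the opioid paragraph of Section 4.2.1. It separates two named opioids that are prohibited, with a pointer to Appendix G, from others that are to be monitored or avoided where possible. The natural inference is that alfentanil and fentanyl belong to the second group. Appendix G says otherwise.

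What is at stake is patient safety. The same paragraph warns that inhibition of opioid metabolism through CYP3A4 "can lead to opioid toxicity, including fatal respiratory depression". A site following this drug-specific text could give a prohibited opioid and believe that it was within protocol. Opioid use on study is foreseeable: the diarrhea guidance in Section 5.3 itself uses opium tincture and dihydrocodeine.

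**Working it through.** No plan figure is involved. The check sets the texts side by side and then bounds the period in which they can conflict.

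**Step 1. Opioid by opioid**

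| Opioid | Appendix G | Section 4.2.1 | Agreement |
|---|---|---|---|
| Methadone | Prohibited (known-TdP row) | Prohibited, cites Appendix G | Yes |
| Levomethadyl | Prohibited (known-TdP row; also sensitive CYP3A substrates) | Prohibited, cites Appendix G | Yes |
| Alfentanil | Prohibited (narrow-index CYP3A row) | Avoid where possible | No: direct conflict |
| Fentanyl | Prohibited (narrow-index CYP3A row) | Named as interacting; class is monitored | Misleading by omission |

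Section 4.2.1 states the prohibition for 2 of 4. Alfentanil has two incompatible drug-specific rules. For fentanyl there is one rule, in Appendix G, and a paragraph that omits it.

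**Step 2. Does other text remove the mismatch?**

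- *Opening of 4.2.* It makes permission subject to Appendix G. That settles which text should prevail, but a weaker alfentanil rule still stands in the same section.
- *Exclusion 3.2.12.* This is an entry criterion. It does not address an opioid started on study.
- *Appendix F, footnote 1.* This gives precedence to Appendix G only for drugs on the Appendix F list. Neither alfentanil nor fentanyl is on that list as reproduced, so the footnote does not reach them.
- *The discretion sentence in 4.2.1.* It makes no exception for Appendix G and points to Appendix F, although the narrow-index CYP3A substrates are listed in Appendix G.

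**Step 3. The window**

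Section 4.1 gives BYL719 daily from the first to the last of 28 radiation fractions. With a Monday start and no breaks:

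- 25 fractions in 5 weeks end on day 33.
- The remaining 3 fall on days 36, 37 and 38.
- 38 / 7 = 5.4 weeks, in line with the 5½ weeks in Section 5.1.

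Surgery follows 6–10 weeks after the last treatment: 6 × 7 = 42 to 10 × 7 = 70 days. Opioids given at the resection are therefore outside the period in which Appendix G applies. Section 17.0 plans approximately 24 patients.

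**The case against.** The best answer is that the protocol already says which text controls. Section 4.2 opens by subjecting everything below it to Appendix G, and the appendix title is unambiguous. On fentanyl, describing an interaction is not granting permission. Class-wide monitoring is compatible with bans on individual opioids, as the same paragraph shows by banning two. Section 4.2.1 never says that those two are the only ones. Concomitant medications are also reviewed weekly during radiation (Section 6.0), and patients must report new ones (Section 4.2).

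Much of this stands. Appendix G does govern, and fentanyl is a misleading omission, not a contradiction. But the alfentanil sentence cannot be read as a ban, and a general precedence clause is weak protection when the drug-specific instruction says something softer. Weekly review would usually find the drug after it had been started.

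A reader might also infer that Section 4.2.2 leaves no rule for holding BYL719 when one of these two opioids is needed, because its explanatory clause describes drugs with known TdP risk and neither opioid is in that row. The documents do not support that. The literal trigger is any medication in Appendix G, which includes both. The same paragraph goes on to note that Appendix G also prohibits CYP3A and CYP2C substrates with possible or conditional TdP risk. The explanatory clause is loosely worded, but it does not show that the hold fails to apply.

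**Conclusion.** The point holds for Section 4.2.1 alone. Its instruction on alfentanil conflicts with Appendix G, and its treatment of fentanyl invites a reading that Appendix G rules out. Since Sections 4.2 and 3.2.12 indicate that Appendix G governs, 4.2.1 is the text to correct.

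The size is modest: two of four prohibited opioids, started during roughly 38 days of BYL719 per patient, in about 24 patients. The documents give no frequency of alfentanil or fentanyl use, so the number of patients at risk cannot be estimated.

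This rests on three assumptions: the two spellings of alfentanil denote one drug, radiation runs without interruption from a Monday, and Appendix G reflects the sponsor's intent. If the sponsor in fact wants monitored use, Appendix G would have to change instead; both texts cannot stand.

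A reader might infer an effect on the maximum tolerated dose, on the scoring of dose-limiting toxicity or on evaluability. Nothing in the documents establishes one. This is an internal inconsistency in a safety instruction, worth correcting for that reason.

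**What to change.** Make two edits in Section 4.2.1:

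1. Replace the alfentanil sentence and the methadone/levomethadyl sentence with: *The use of methadone, levomethadyl, alfentanil and fentanyl is prohibited during BYL719 (refer to Appendix G).* Use the Appendix G spelling throughout. The sentence listing interacting opioids can stay as a description once the ban is explicit.
2. In the sentence giving investigators discretion over CYP substrates, add: *except drugs listed in Appendix G.*

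Do not add a hold in Section 4.2.2 specific to alfentanil and fentanyl. The existing trigger already reaches them. Naming two drugs would suggest that the other Appendix G drugs without known TdP risk need no hold. It would also raise a question under the 67% evaluability rule, which exempts shortfalls required by the protocol: on a 38-day course, a 13-day hold leaves (38 − 13) / 38 = 25 / 38 = 65.8% of BYL719 doses.

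The cost is a wording amendment and a notice to sites. The clinical downside is a narrower choice of opioids during BYL719. No assessments are added, and the sample size and the dose-escalation rules do not change.

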Appendix H: CAPECITABINE DOSING TABLE BASED UPON BODY SURFACE AREA CALCULATION

Dosing Table Based Upon Body Surface Area Calculation: Capecitabine Starting Dose

	2	AM	AM	PM	
Dose level 1650	0 mg/m ² /d	150 mg	500 mg	150 mg	PM 500 mg
BSA (m ²)	Total Daily Dose (mg)				
<1.24	2000	0	2	0	2
1.25-1.36	2150	1	2	0	2
1.37-1.51	2300	1	2	1	2
1.52-1.64	2600	2	2	2	2
1.65-1.76	2800	1	3	1	2
1.77-1.91	3000	0	3	0	3
1.92-2.04	3150	1	3	0	3
2.05-2.17	3300	1	3	1	3
>2.18	3600	2	3	2	3
